intranasal doses of ketamine at 10 mg, 30 mg and 50 mg ²⁸. Therefore, for study purposes 10mg, 30 mg and 50mg of intranasal ketamine will be administered. Each visit will be two to seven days apart to avoid any accumulation of study doses. Subjects will be recruited at the supportive oncology clinic, oncology clinics, the pain clinic and Acute Pain Service at Emory. Subjects may be identified and contacted via telephone with information about the study prior to their next clinic appointment in order to allow time for them to consider the study. After informed consent has been obtained, study eligibility will be confirmed (see Table of Assessments). An appointment will be made for the Phase I Unit at Winship. A family member/friend must transport the patient home following drug administration, as driving for 24 hours post drug administration is discouraged. Written informed consent will be obtained prior to performance of study procedures, either while recruiting prior to study visit one or during the first study visit, prior to beginning the study. Subjects must meet all study eligibility criteria on Visit 1 prior to study treatment. Patients will be asked to return to the Phase 1 Unit for a total of 5 study visits. All study visits to the clinic will take place within six weeks or less. A telephone call visit will occur 14 days after the last dose of medication administered to follow any ongoing adverse events that occurred during the study period. If there are no ongoing adverse events at the end of visit five, the subject's participation will end at that time. Subjects may be reconsented if withdrawn early, at the discretion of the investigator, provided all eligibility requirements are met.

Table of Assessments

Assessments	Screening	Visit One	Visit Two	Visit Three	Visit Four	Visit Five	Telephone Call
Review of Inclusion/Exclusion	X						
Informed Consent	X						
Med Hx/Demographics	X						
Hemoglobin (if none within 3 months of Visit One)		X					
Urine pregnancy test-within one week of planned Visit (women of child bearing potential)		X	X	X	X	X	
PHQ9 Depression Screening	X	X ¹					
Completion of PROMIS Questionnaire		X				X	
ECOG score		X	X	X	X	X	
ESAS		X	X	X	X	X	
MADRS ^{2,3}		X	X	X	X	X	
Height		X					
Weight		X	X	X	X	X	
IV access		X	X ⁴	X	X		
Study Medication Administration		X	X	X	X		
Vital Signs(HR ⁵ , BP, RR, Pulse Oximetry ⁶)		X ⁷	X ⁷	X ⁷	X ⁷	X ⁸	
Blood Samples (PK)		X ⁹	X ^{9,10}	X ^{9,10}	X ^{9,10}	X ¹⁰	
Hepatic Function test		X				X	

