- Side effects as noted on the SERSDA scale are valued as 2 or less, or no more than 1 point greater than their baseline value. Investigator must be notified if value is greater than 2.

Should the patient not meet these criteria at the end of the 240 minute assessments, the study nurse will contact the research physician for further evaluation and assessment.

C.4 Potential Risks

Adverse effects are dose related. No serious side effects have been reported with intranasal ketamine doses of up to 50 mg.

Common side effects of ketamine: Include sedation, somnolence, sensory illusions, dissociative feelings, blurred vision, anorexia, abdominal pain ^{38, 39}, feeling of insobriety ^{40, 41}, and dream disturbances ⁴². Dose-dependent side effects include hallucinations, agitation, nightmares, dizziness, and nausea ⁴³. At higher doses, side effects may include delirium, impaired motor function, amnesia, anxiety, panic attacks, mania, insomnia, and elevated blood pressure ⁴³. Rarely, hepatic failure⁴³ has been reported in participants with

underlying liver disease prior to ketamine administration. Additionally, chronic administration of ketamine has been associated with ulcerative or hemorrhagic cystitis, which usually resolves with cessation of ketamine administration⁴³. However this was reported in ketamine abusers and dosage being used for this study are very low. Additionally, a LFT and UA will be done the day of or up to 24 hours before both visits 1 and 5 to monitor for rare side effects. If obtained as standard of care within this time frame, these will not need to be repeated for the study. Benzodiazepines and neuroleptics have been used to successfully minimize psychotomimetic effects, such as psychosis or delirium, when ketamine is used for the treatment of pain^{44, 45}.

C.5 Management of specific side effects

Side effects unique to intranasal route: Include transient change in taste, rhinorrhea and nasal passage irritation. If the patient reports that these changes to be persistent beyond the date of administration of study drug and are moderate to severe in intensity, then a formal ENT consult will be sought.

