Cardiovascular effects: Potential effects include: increases in heart rate, systemic arterial pressure, systemic vascular resistance, pulmonary artery pressure, and pulmonary vascular resistance. In the absence of autonomic control, ketamine has direct myocardial depressant effect, usually overridden by central response. If >20% variation from baseline is noted in heart rate or blood pressure, study MD will be notified. Risk assessment will be done by the MD and appropriate medications will be given as deemed necessary. Patient will be admitted to inpatient medical oncology service for 23 hours observation if at the end of study visit a >20% variation persists despite treatment; HR >120; hypertensive urgency/emergence occurs. Hypertensive urgency is defined at SBP>180 or DBP>110. In hypertensive emergency signs or symptoms of end organ damage are noted such as blurry vision, headache, and chest pain.

Central nervous system effects: Include- tremors, increased intracranial pressure, floating sensation, hallucinations (auditory and visual), delirium, vivid dreams or illusions, confusion, restlessness, disorientation, dysphoria, dizziness, and sedation. After discontinuation of ketamine, recurrent illusions (flashbacks) can occur. Ketamine can lower the seizure threshold, especially in patients on aminophylline. Benzodiazepines such as midazolam 0.5 mg to 5 mg IV or lorazepam 0.5 mg to 5 mg IV or diazepam 0.5 mg to 10 mg IV or oral, etc. may be given to mitigate CNS side effects at the discretion of the study MD. Admission for 23 hours observation to the inpatient medical oncology service will be considered if at the end of a study visit either excessive sedation is noted or RASS score between -3 and -5 or if any severe psychological manifestations exist.

Gastrointestinal system effects: Include nausea, vomiting and increased salivation (due to increased salivary and tracheobronchial mucous gland secretions). Nausea and/or vomiting will be treated with

ondansetron 4 to 8 mg IV or PO depending upon severity. Diphenhydramine 6.25 to 25mg IV may be given, if no relief from ondansetron or if ondansetron is contraindicated. For increased salivation, not well tolerated by the patient, glycopyrrolate 0.2mg IV may be given if deemed necessary by the study MD. Admit if unable to tolerate oral liquid at the end of visit.

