Respiratory effects: Respiratory depression is rare (ventilator response to CO₂ is maintained). Upper airway skeletal muscle tone is maintained; upper airway reflexes remain relatively intact. Respiratory depression can occur when ketamine is given in conjunction with other agents (e.g. opioids) or when given in large doses or rapid infusions. Treatment may include: decrease/stop opioids and other sedating medications. If respiratory depression (RR < 10/min, O₂ sat < 90%) persists at the end of the study visit, the study MD will be notified and potential admission will be considered, the patient's will be admitted for 23 hour observation with the inpatient oncology service.

Ocular effects: Nystagmus (especially vertical nystagmus), diplopia, blurred vision and slight elevation in intraocular pressure are possible. If this happens at the end of the study visit, the study MD will evaluate for safeness for discharge vs 23 hrs observation.

Musculoskeletal effects: There is a possibility of increased skeletal tone or tonic-clonic movements. The study MD notified if this happens. This will be monitored and treated appropriately. Short acting benzodiazepines like IV midazolam may be considered.

Allergic reaction: Ketamine does not evoke histamine release; and, rarely, if ever causes allergic reaction. If an allergic reaction is suspected then the reaction will be treated based on the severity, with steroids and antihistamine allergic agents.

C.6 Benefits:

The patient may benefit from improved pain control and improved mood or depression control by participating in this research study.

C.7 Participant selection:

A sample size of 7 from a population of 20 (in the study done by Carr et al.) achieves 91% power to detect a NPRS difference of -2.7 between the null hypothesis mean of 0.0 and the alternative hypothesis mean of 2.7 with an estimated standard deviation of 1.9 and with a significance level (alpha) of 0.05000 using a two-sided Wilcoxon test assuming that the actual distribution is normal.

We need a sample size of 7 patients based on statistical analysis observed in the study done by Carr. We will include 10 patients to account for the possibility that the observed pain reduction in the current study may be different than the study done by Carr, as in this study patients were given ketamine for breakthrough pain,

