as opposed to for baseline pain. We will enroll up to 25 patients in the study to account for potential dropouts. If a higher dropout rate is observed, then we will enroll more patients until we have at least 10 patients who complete the entire study.

Subject Replacement

Any subject who does not complete the IV dosing and at least one intranasal dose will be replaced and followed for safety as needed and/or via telephone call at 14 days.

Enrolled subjects who discontinue early will be replaced.

If a subject misses more than one treatment visit during the study period, the subject will be withdrawn and replaced to achieve a minimum of 10 subjects who are maximally treated with study medication (4 study visits).

The patients should meet the following inclusion and exclusion criteria.

C.8 Inclusion Criteria: Patients will be eligible to participate if they are:

1. Male and female subjects at least 18 years of age
2. Patients with uncontrolled pain related to cancer or cancer treatment. Uncontrolled pain will be defined as ^{46,47}
 - i. pain which persists for more than 7 days and is rated $>/=4$ on NPRS
 - ii. use of breakthrough medication more than 4 times in 24 hours or being treated with oral morphine equivalent of 50 mg/d or more
3. Patients who are⁴⁸ able to follow-up in person during the trial
4. Patient on stable analgesic regimen for >7 days without escalation during study period with rescue or immediate release medication every 3 hours or longer
5. Patients who are willing and able to maintain a daily pain diary
6. Patients who are able to understand written and verbal English
7. Patient weight $>/= 50$ kg

C.9 Exclusion Criteria: Patients will be excluded from the study if they have any of the following:

1. Transportation issues interfering with return study visits
2. Patients with high disposition of laryngospasm or apnea
3. Presence of severe cardiac disease

4. Presence of conditions where significant elevations in blood pressure would be a serious hazard.
5. Stage 2 hypertension or greater (systolic blood pressure > 160 and/or diastolic blood pressure >100)
6. Baseline tachycardia, HR >100
7. History of seizures, elevated ICP or CSF obstructive states(e.g. severe head injury, central congenital or mass lesions)
8. Conditions that may increase intraocular pressure (e.g. glaucoma, acute globe injury)
9. History of uncontrolled depression or other psychiatric comorbidity with psychosis
10. History of liver disease

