11. History of interstitial cystitis
12. History of nasal or sinus anomalies or dysfunction e.g. allergic or infectious rhinitis.
13. Patients with lesions to the nasal mucosa
14. Pregnant women, nursing mothers and women of childbearing potential not using contraception known to be highly effective. Highly effective contraception methods include combination of any two of the following:
 - i. Use of oral, injected or implanted hormonal methods of contraception or;
 - ii. Placement of an intrauterine device (IUD) or intrauterine system (IUS);
 - iii. Barrier methods of contraception: condom or occlusive cap (diaphragm or cervical/vault caps) with spermicidal foam/gel/film/cream/ vaginal suppository;
 - iv. Total abstinence;
 - v. Male/female sterilization.
15. Illicit substance abuse within the past 6 months
16. Documented history of medication abuse/misuse (e.g. Unsanctioned dose escalation, broken opioid agreement etc.)
17. Clinical requirement for medications that are concurrent inducers or strong inhibitors of CYP3A4. CYP3A4 substrates are allowed. (Appendix II-D)
18. Porphyria (possibility of triggering a porphyric reaction)
19. Severe active anemia (a hemoglobin< 8 documented by labs drawn within 3 months of first study treatment)
20. History of difficult intravenous access
21. Intractable vomiting

C.10 Informed Consent Process:

Informed consent will be obtained by a research team member delegated to do so by the PI, prior to conducting any research procedures. This process will include a discussion of risks and benefits, as well as answering patient questions. If patients are able to provide their own medical history, they will be deemed capable of providing informed consent for research participation. The process will be free of coercion. Study patients will be paid a small amount to reimburse for travel expenses for each visit completed. They can withdraw at any time without penalty to their ongoing care.

C.11 Compensation for time and effort:

A compensation of \$50 per visit will occur with each patient for each completed visit to reimburse for travel expenses to and from the institution.

C.12 Statistical analysis:

Study results will be analyzed as below to achieve the study objectives:

1. Determine pharmacokinetics of intranasal ketamine.

Concentrations of ketamine and its metabolite norketamine will be analyzed to determine pharmacokinetic characteristics such as bioavailability, peak effect and elimination.

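### C.5 names patients on aminophylline as at particular risk of a lowered seizure threshold, but no criterion in C.8 or C.9 keeps such a patient from being dosed

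*Combined protocol and SAP*

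**What the plan says.** The warning stands in C.5 Management of specific side effects, under Central nervous system effects: "Ketamine can lower the seizure threshold, especially in patients on aminophylline". It is the only mention of aminophylline in the documents.

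C.9 Exclusion Criteria has two items that bear on it:
- Item 7, the only seizure-related criterion, begins "History of seizures, elevated ICP or CSF obstructive". Everything it lists is a condition or a history.
- Item 17, the only exclusion based on a current prescribed co-medication, reads "Clinical requirement for medications that are concurrent inducers or strong inhibitors of CYP3A4. CYP3A4 substrates are allowed" and refers to the chart in Appendix II-D.

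On timing, C.2 Methods states: "Subjects must meet all study eligibility criteria on Visit 1 prior to study treatment".

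The response to an event is in C.5. Benzodiazepines "may be given to mitigate CNS side effects at the discretion of the study MD". Under Musculoskeletal effects the plan says "There is a possibility of increased skeletal tone or tonic-clonic movements", requires that the study physician be told, and adds "Short acting benzodiazepines like IV midazolam may be considered".

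The Dose Finding paragraph gives 10 mg intranasally at Visit 1 as a tolerance dose and 10 mg IV at Visit 2. The 30 mg and 50 mg intranasal doses at Visits 3 and 4 are given only if smaller doses caused no severe adverse events.

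**The concern.** The protocol identifies a subgroup at heightened risk of a specific harm, and the subgroup is defined by a drug that can be asked about before dosing. The eligibility rules do not use that information. Staff who follow C.8 and C.9 exactly would enrol and dose a patient whom C.5 singles out. Medical history at screening would probably reveal the drug, but no rule then tells the investigator what to do about it.

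What is at stake is individual patient safety and agreement between the protocol's warning and its criteria. Sample size, power, alpha and endpoints are not involved.

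**Working it through.** No arithmetic beyond counting applies, and the plan states no figure to reproduce. The check sets the warning against every place where it could have been acted on before dosing.

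**1. Eligibility criteria.** C.8 has 7 items and C.9 has 21, so 28 in all. Read one by one, 0 of 28 are triggered by aminophylline.
- Item 7 works by condition, so it does not reach a patient on the drug with no seizure history, raised intracranial pressure or CSF obstruction.
- Item 17 works by CYP3A4 effect. Aminophylline is not among the substrates, inhibitors or inducers in Appendix II-D.
- Items 15 and 16 concern substance abuse and medication misuse.
- The medication terms in C.8 concern analgesics only.
- Items 2 (laryngospasm or apnea), 3 (severe cardiac disease) or 6 (tachycardia) might remove some users incidentally, but none targets the drug.

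**2. How C.9 treats comparable hazards.** Most ketamine hazards described in C.4 and C.5 have a matching exclusion:

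| Hazard in C.4 or C.5 | Exclusion in C.9 |
|---|---|
| Cardiovascular effects | Items 3 to 6 |
| Raised intracranial pressure; seizures | Item 7, by condition |
| Raised intraocular pressure | Item 8 |
| Psychiatric effects | Item 9 |
| Liver injury | Item 10 |
| Cystitis | Item 11 |
| Lower seizure threshold with aminophylline | None |

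**3. Checks at the visit, before dosing.** C.3 has 5 physician-notification items, and none concerns aminophylline. The pre-dose trigger (item 1) is heart rate, blood pressure or a low pain score, and the physician then decides by the eligibility criteria, which omit the drug. Of the 17 documentation items in C.3, only item 15 cancels a visit. It covers symptoms of respiratory infection, at Visits 1, 3 and 4. Item 13 records a change in health status but triggers no hold. Full eligibility is tied to Visit 1, so no stated rule covers a patient who starts the drug between visits.

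**4. What limits exposure.**
- The Dose Finding condition stands before the 30 mg and 50 mg doses. It does not protect the first 10 mg dose, and as worded it applies to Visits 3 and 4, not to the IV dose at Visit 2.
- Heart rate and pulse oximetry are monitored continuously for at least 30 minutes, and assessments run to 240 minutes.
- Benzodiazepines and the response to tonic-clonic movements are available after an event.
- Under C.13 item 6, one drug-related hospitalization puts the study on hold for review, and more than one ends it.

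**5. Number of patients.** The plan seeks 10 completers and allows up to 25 enrolled, with more if dropout is high. It gives no rate of aminophylline use. The affected number could be anything from 0 to 25 of the planned enrolment, and nothing in the documents narrows that range. That it would be near 0 is a judgement, not a result.

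**The case against.** The strongest reply is that a risk statement is not a contraindication. C.5 describes possible effects and how to manage them. It nowhere says that aminophylline users must not be dosed. The same section notes that respiratory depression can occur when ketamine is combined with opioids, yet C.8 item 2 admits patients on 50 mg/day or more of oral morphine equivalent. On this view the protocol's approach is to name an interaction, monitor and treat.

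Part of this stands. A reader might infer that C.5 and C.9 contradict each other, and they do not: no rule forbids what another allows. The opioid comparison does not carry the rest. Opioid or breakthrough-medication use defines this population, so opioids could not be excluded. No such reason applies to aminophylline.

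A second reply is that safeguards do act before dosing. This is right for the two highest doses. A reader who inferred that nothing stands between such a patient and 50 mg would be wrong, because the dose-finding condition comes first. It leaves the first 10 mg dose open.

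A third reply is that no harm has been shown. C.4 states "No serious side effects have been reported with intranasal ketamine doses of up to 50 mg". That limits the weight of the point. It does not settle it, since the statement covers the intranasal route only and does not mention aminophylline users.

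**Conclusion.** The gap is real and minor. As written, a patient on aminophylline with no seizure history who meets the other criteria is eligible and can receive the first 10 mg dose, although C.5 singles that patient out. Confidence is high for this reading of the text, because C.8 and C.9 are visible in full.

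The documents do not support a claim that such patients are likely to have seizures in this trial, or that the trial is unsafe. They give no rate of use, no seizure rate and no size for the interaction at 10 to 50 mg, so expected harm cannot be estimated. The conclusion rests on the visible protocol. The package insert is reproduced only in part and the study-specific operating procedure is not included, but neither would take the place of a criterion in C.9. The point is best treated as a cheap improvement.

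**What to change.** Add one exclusion to C.9: *Current use of aminophylline (seizure-threshold interaction with ketamine, see C.5).*

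Add one line to C.3: at each dosing visit (Visits 1 to 4), ask whether aminophylline has been started. If it has, notify the study physician before dosing, and do not dose while the patient is taking it. Visit 2 belongs in the rule because the C.5 warning is not limited to one route. The documents name no other drug in this connection, so the line is confined to aminophylline.

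The cost is small. Item 17 already requires a look at current medication at entry, and the later question is asked at visits already held. The downside is a rare lost recruit or delayed visit. C.7 already replaces enrolled subjects who discontinue early. A delayed visit must still fit the six-week window in C.2; the stated purpose of the two-to-seven-day spacing is to avoid accumulation, which a longer gap does not worsen.

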- 3) Higher bioavailability compared to oral route due to absence of hepatic first pass effect; and

- 4) Large surface area, uniform temperature, high permeability and extensive vascularity of the nasal mucosa facilitate rapid systemic absorption of intranasal administered drugs [19].

Intranasal ketamine has been shown to be effective in controlling breakthrough pain in a double blind randomized control trial (DBRCT) performed by Carr in 2003, as well as help with depression in a DBRCT by Lapidus in 2014^{20,21}. Both studies were NIH funded. The Carr study was a DBRCT in 20 patients with breakthrough pain and noted pain relief within 10 min, lasting up to 60 minutes with 10-50 mg of intranasal ketamine (2.65 point average decrease on NPRS scale). The pain scores were only recorded until 60 minutes after the drug administration and the patients were allowed to determine the dose themselves, without precise description for this in the study. Lapidus study was performed in 20 patients with major depression and noted significant improvement in depressive symptoms (7.6 point average decrease on MADRS scale) in 44% of patients at 24hrs with 50mg of intranasal ketamine. There are limited data regarding the use of ketamine as an adjuvant to opioids for the management of *cancer* pain²². We seek to obtain preliminary data on safety, feasibility, and utility of this novel technique for the treatment of uncontrolled cancer pain. Ketamine is a scheduled III medication. Intranasal ketamine can be ordered by a physician from a compounding pharmacy.

A2. Pharmacokinetics:

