2. Determine pharmacodynamics of intranasal ketamine in terms of Patient Reported Outcomes

- i. Pain scores on NPRS will be analyzed by Wilcoxon signed-rank test as the study sample size is too small to be analyzed by paired t test. Generalized Linear Model will be used to model any time trend for pain score change and to test if the trend is significant.
- ii. T-test will be used to compare any changes in depression severity on MADRS.
- iii. Chi-square test will be used to test presence/absence of any side effects. Wilcoxon signed rank test will be used to assess the severity of all the side effects (including SERSDA), if needed.
- iv. Paired T-test will be used to asses any changes in functional status on PROMIS scale.
- v. T-test will be used to compare any changes in ESAS and ECOG.

3. Determine PK-PD relationships of NAS ketamine delivered

Timing, degree and duration of change in pain scores will be compared with individual and group pharmacokinetic parameters to assess potential relationships between measures of exposure (C_{max} , and AUC_{0-t}) and pain relief. Multivariate modeling including patient-specific data (age, sex, weight, BMI, morphine equivalents) will be performed using initial PK parameters and goodness of fit analyses for compartmental model selection. If applicable, data from vital sign measurement changes will also be used as comparison with pharmacokinetic data.

4. Determine opioid sparing effect of intranasal ketamine.

- i. Chi-square test will be used to compare frequency of rescue medication use.
- ii. T-test will be used to compare total opioid consumption.

C.13 Data and Safety Monitoring and Reporting Plan:

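### The 91% power stated for 7 patients does not follow from its inputs: the planned test has about 85% at 7 and about 97% at the 10 completers planned

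*Combined protocol and SAP*

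**What the plan says.** Section C.7 (Participant selection) opens its justification with "A sample size of 7 from a population of 20", the 20 being attributed to the earlier intranasal ketamine trial. It says that this number "achieves 91% power to detect a NPRS difference of -2.7 between the null hypothesis mean of 0.0 and the alternative hypothesis mean of 2.7", taking an SD of 1.9 and alpha 0.05, "using a two-sided Wilcoxon test assuming that the actual distribution is normal". It concludes that 7 patients are needed.

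It then raises the number: "We will include 10 patients to account for the possibility that the observed pain reduction in the current study may be different", because the earlier trial treated breakthrough pain and this one treats baseline pain. Up to 25 patients may be enrolled, and enrolment goes on "until we have at least 10 patients who complete the entire study". No power is given for 10.

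Section A1 (Background) describes the earlier trial as a "DBRCT in 20 patients with breakthrough pain" and gives its effect as a "2.65 point average decrease on NPRS scale". The analysis in C.12 matches the test in C.7: "Pain scores on NPRS will be analyzed by Wilcoxon signed-rank test".

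**The concern.** A sample size calculation that names both a sample and a finite population usually shrinks the standard error, because sampling a large share of a closed group leaves less uncertainty about that group. Here the closed group would be the 20 patients of a completed trial. This trial does not sample from them. Under C.2 it recruits new patients from oncology, supportive oncology and pain services, and its results are meant to apply to cancer pain patients in general. Any such shrinkage would overstate power.

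The 91% is the only power figure in the text, and the statement that 7 patients are needed rests on it. The protocol also gives no power for the 10 completers it commits to, and does not say how much smaller a pain reduction the three extra patients would cover.

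**Working it through.** **Inputs.** From C.7: n = 7, N = 20, mean change 2.7 against 0, SD 1.9, two-sided alpha 0.05, one-sample Wilcoxon test, normal data. From C.7 also: at least 10 completers. From A1: unrounded effect 2.65. From C.2 (Dose Finding): the lowest cutoff for clinical relevance, 2.4 points.

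**Step 1: look for the printed 91%.** A common approximation for the Wilcoxon test on normal data multiplies n by 3/π and uses the noncentral t distribution. For 7 patients the effective n is 7 × 3/π = 6.68.

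- With a finite-population correction and the effective n cut to 6: SD = 1.9 × √(1 − 6/20) = 1.590; noncentrality = 2.7 × √6 / 1.590 = 4.16; critical t on 5 df = 2.571; power = **90.9%**, which rounds to 91%.
- The same n = 6 without the correction: noncentrality = 2.7 × √6 / 1.9 = 3.48; power = 79.3%.
- Other forms of the correction with n cut to 6 give 89.5% to 92.7%. Without the cut (n = 6.68 or 7) they give 93.7% to 97.0%.

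The printed figure is thus reproduced with a population of 20 and the effective n rounded down. The protocol states neither step, so the route is an inference.

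**Step 2: power at 7 without the correction.**

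- Efficiency-adjusted t: noncentrality = 2.7 × √6.68 / 1.9 = 3.67. Power is 85.4% with df = 5.68 (effective n − 1) and 86.2% with df = 6 (n − 1).
- Exact signed-rank test: the two-sided test rejects when the smaller rank sum is 2 or less. Of the 2⁷ = 128 sign patterns, 3 give a sum of 2 or less on one side, so the size is 2 × 3/128 = 0.0469. Simulated power on normal data (2,000,000 samples) is **84.6%**.
- Plain paired t test, for comparison: noncentrality = 2.7 × √7 / 1.9 = 3.76; power 87.7%.

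All are below 91%.

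**Step 3: can rounding of the inputs explain it?** The most favourable values that round to the printed ones are a mean of 2.75 and an SD of 1.85. They give 87.5% by the exact test and 88.3% to 89.0% by the efficiency-adjusted t. The unrounded effect in A1, 2.65, moves the other way: 83.3% by the exact test.

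**Step 4: power at the 10 completers planned.** The exact test rejects when the smaller rank sum is 8 or less; its size is 2 × 25/1024 = 0.0488. The effective n is 10 × 3/π = 9.55.

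| True mean reduction (SD 1.9) | Exact, n = 7 | Exact, n = 10 | Efficiency-adjusted t, n = 10 |
|---|---|---|---|
| 2.7 | 84.6% | 97.2% | 97.1% to 97.3% |
| 2.65 | 83.3% | 96.7% | 96.6% to 96.8% |
| 2.4 | 75.9% | 93.2% | 93.0% to 93.4% |
| 2.3 | – | 91.2% | 90.9% to 91.3% |
| 2.0 | – | 82.4% | – |

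Ten completers therefore keep the printed 91% down to a true reduction of about 2.3 points.

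**The case against.** **The cause is not proven.** The mention of 20 patients could be no more than a clumsy citation of where the effect came from. The match to 91% needs two unstated steps, and other routes come close: the exact test at 7 with a one-sided cutoff (rank sum 3 or less) gives 91.9%, and the efficiency-adjusted t at n = 8 gives 91.3%. This is fair as to the mechanism. But those rivals contradict the protocol's own two-sided test and its 7 patients, and whichever route was used, the stated inputs do not give 91%.

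**Nothing in the trial depends on it.** Seven is not the target, replacement continues until 10 complete, about 85% is not low, and the stated purpose is preliminary data, with pharmacokinetics as the first aim. This stands, and it is why the point is minor.

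**The sensitivity figures could be over-read.** C.2 says the relevance cutoff depends on baseline pain and ranges from 2.4 to 5.3. Rejecting a mean change of zero does not show a clinically relevant change. This also stands: the 93% at 2.4 points is power to detect some reduction if the true mean is 2.4, and no more.

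**The corrected figures share the limits of the printed one.** They assume continuous normal changes, although the pain scale is scored in whole numbers and will produce ties. They also refer to one comparison, while C.12 does not say which dose or post-dose time is tested. This is true of both sets of figures and does not narrow the gap between them.

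**Conclusion.** The concern holds, at minor severity. On the protocol's own inputs the two-sided Wilcoxon signed-rank test has about 85% power with 7 patients, not 91%, an overstatement of about 5 to 6 points that rounding does not explain. A finite-population correction is the likely source but is inferred. It would not apply here in any case, because the patients are not sampled from the 20 in the earlier trial.

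The target of at least 10 completers is not in question: power there is about 97% for a reduction of 2.7 and about 93% for 2.4. These figures rest on SD 1.9, normally distributed changes, two-sided alpha 0.05 and a single before-and-after comparison.

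**What to change.** In C.7, delete the reference to a population of 20 and cite the earlier trial only as the source of the mean reduction and the SD. Replace the power statement with wording to this effect:

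> With a mean NPRS reduction of 2.7 and an SD of 1.9, the two-sided Wilcoxon signed-rank test at alpha 0.05 has about 85% power with 7 patients and about 97% with 10 completers, assuming normally distributed changes. If the true mean reduction is 2.4 points, 10 completers give about 93%; at 2.3 points, about 91%.

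The last sentence is optional. It gives the protocol's reason for adding three patients a figure, but should not be presented as evidence of clinical relevance. Keep the target of 10 completers.

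The cost is one paragraph of wording. The sample size, test and endpoint do not change. The figure for 7 patients becomes less favourable, and the figure for the number actually planned is higher than the one now printed.
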